Intervention: TAU will consist of routine, weekly mental health psychotherapy as all participants must have a referring mental health provider to be eligible for this pilot RCT. The CCT rehabilitation model aims to teach individuals strategies that allow them to work around cognitive deficits. CCT provides training in compensatory attention and learning/memory skills, formal problem-solving strategies applied to daily problems, and the use of external aids, such as calendar systems and assistive devices to promote completion of daily tasks ([name] et al., 2016). CCT sessions consists of interactive didactic information and discussion, and activities that introduce a variety of cognitive strategies and external aids. Participants are given a copy of the treatment manual and a paper calendar or day planner if requested, or they may request training on a smartphone or electronic calendar system instead. They will receive extensive graduated training in and practice with their chosen calendar system across sessions with a focus on how the day planners can facilitate the use of compensatory strategies taught each week. [name] will supervise the CCT groups run by the study coordinator, co-facilitating early groups as needed for training purposes. They have an ongoing relationship with local psychology doctoral programs which may provide clinical trainees who may provide supervised group facilitation. The current CCT Treatment Manual ([name], [name], et al., 2016) is included as an Appendix, though aspects of structure and content will be changed before this pilot RCT for PTSD to tailor the intervention to PTSD rather than TBI. We have successfully tailored CCT to other similar Veteran populations in the past, and we expect to be able to refine it for Veterans with PTSD prior to CDA initiation. We have also had success training a variety of master's level research associates and providers to administer the intervention, and similar training and fidelity monitoring protocols (e.g., recorded sessions, 20% random fidelity checks) previously utilized by Drs. [name], [name], and [name] will be implemented in this proposed efficacy study. The following table outlines the CCT structure and content.

Table of CCT for PTSD Session Content				
Session	Major Concepts	Examples of Strategies	Session Activities	Home Exercise
1	Intro and PTSD/cognitive functioning psychoeducation	Creating a "home" for important items	Day planner use	Finding a home for the day planner

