Randomization and Blinding: All eligible participants will be randomized to either the CCT or TAU group. Randomization tables will be prepared by the study statistician at the beginning of the study and assignments to CCT or TAU will be based on the randomization table. New participants will be allocated to the current group awaiting randomization. Once group membership reaches 6 participants, the group will be randomized by the statistician. We will employ a system of adaptive randomization, weighted to achieve the desired proportion of participants in each condition, managed by the statistician. Randomization will be implemented by the study coordinator in coordination with the statistician who will monitor randomization procedures. Because of the small sample size and number of study personnel in this pilot RCT, it might not be feasible to blind the assessor to participant group status if the assessor is also co-facilitating CCT groups with [name], though this type of blinding will be implemented if possible.

Data Analysis: Rates of recruitment, retention, and participation will be calculated, and we will compare participant characteristics at baseline by group (CCT vs. TAU). We will conduct intent-to-treat analyses to compare change from baseline to 3-month follow-up within and between groups.

Study Feasibility Analyses: Descriptive statistics will characterize the feasibility of recruiting and retaining Veterans. Recruitment will be deemed feasible if we successfully screen for eligibility 50% of Veterans referred to the study and enroll 75% of screened Veterans who meet all study inclusion criteria. Retention will be deemed successful if we achieve 80% completion for post-treatment assessments. Chi-square tests of association for categorical variables and t-tests for continuous variables will compare demographic and clinical characteristics of successfully versus unsuccessfully recruited and retained Veterans to identify characteristics of participants who may require more intensive recruitment or retention efforts in a future trial.

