In this pilot study, we will first examine descriptive statistics, and conduct tests of normality and homogeneity of variance for variables included in repeated measures analyses. We will examine missing data for all variables and dropout rates in order to plan for a future RCT. though will not conduct multiple imputation or other missing data techniques for this pilot study. We will, however, conduct intent to treat analyses, analyzing data from all randomized participants assigned to CCT versus TAU groups, rather than only including completers. Primary outcome analyses will be multilevel models to compare the change over time in cognitive, mental health, functioning, and QOL outcomes for Veterans in the CCT versus TAU groups. If the sample size is too small to run multilevel models, we will run alternative methods such ANOVAs which are more feasible with smaller samples. We will examine how much symptoms change, comparing changes across groups, and also examine clinically significant change in self-reported functional and clinical outcomes. We will compare the change in proportions of Veterans who fall within in "clinically significant impairment" ranges on objective cognitive performance measures before and after CCT versus TAU, characterizing cognitive functioning deficits according to cognitive domains. Because of the small sample size in this pilot RCT, these analyses will rely heavily on descriptive statistics including identifying individuals who score within clinically impaired ranges on objective testing, and who score above clinical cutoffs on self-report measures. Multilevel models or repeated measures analysis of covariance (ANCOVA) models will examine potential moderators including validity tests, service connection status and percent, number of sessions attended, comorbid mental health diagnosis such as PTSD, and demographic variables.

Study Population and Subject Identification/Recruitment

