Enrollment and Assessment Procedures: Prior to enrollment, interested Veterans will be prescreened. The study coordinator will conduct a medical record review to document cognitive symptoms, medical and psychiatric history, and recent treatments and medications. The Neurobehavioral Symptom Inventory (NSI) will be used as a screening tool to determine the presence of moderate or greater cognitive symptoms for eligibility purposes. A brief phone interview will ensure that Veterans are interested in participating and meet eligibility criteria. All participants will be screened to ensure their ability to comprehend study procedures, risks and benefits. We anticipate that up to 500 Veterans will need to be screened in order to achieve the desired sample size of 36-48 Veteran participants in the study. Veterans will be provided the opportunity to have the informed consent materials mailed to them. After the Veteran receives the informed consent materials, a trained study team member will call the Veteran to go through the informed consent procedures and answer any questions. If the Veteran chooses to participate, he or she will sign the informed consent documents and mail them back to [name] using a pre-addressed and stamped envelope. The study assessment will only be scheduled after the hard copy informed consent is received back from the Veteran. Following determination of eligibility, provision of informed consent, and enrollment into the pilot trial, Veterans will initiate the pilot RCT assessments, and, when assigned to the CCT condition, the 10-week CCT group intervention (weeks 2-11). Cognitive assessments and symptom questionnaires will be completed at baseline, post-treatment (approximately 3-months following baseline), and follow-up (6-months following baseline). Veterans will have the option to complete all study activities, including the 10-week CCT intervention and the 3 cognitive assessments via the VA's telehealth system, VA Video Connect (VVC), or via telephone.

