Participants will be at least 36 (and up to 48) Veterans weighted with more CCT participants (approximately 4-5 CCT groups with 6 Veterans each) than controls (12-18 TAU participants, grouped for randomization piloting purposes into 6-Veteran participants in each of 2 groups). Veterans of all genders, races, and ethnicities will be eligible for this study. We have estimated enrollment for gender, race, and ethnicity based on the recent CCT for mild TBI study, assuming similar demographic proportions. Eligibility will be established by current Mental Health or PTSD Clinic provider and CPRS chart review and will be confirmed by the Veteran during the initial phone call. Eligible Veterans (1) must meet DSM-5 criteria for PTSD based on PTSD or Mental Health Clinic intake assessment or PTSD diagnosis at most recent Mental Health/PTSD clinic visit if intake was completed over 6 months prior to study participation; (2) are patients in the PTSD specialty clinic or Mental Health clinic with a current mental health provider who is willing to provide TAU if randomized as such; (3) prior EBP treatment within the past 2 years confirmed by patients, their current Mental Health or PTSD clinic provider, and a review of CPRS records; (4) do not have a history of TBI of any severity; (5) are able to provide informed consent; (6) are English speaking; (7) are able to travel to the clinics for appointments; (8) do not have auditory or visual impairments that would compromise assessments; (9) do not meet criteria for a substance dependence disorder with less than 30 days abstinence; (10) do not meet criteria for bipolar disorder or psychotic disorders; (11) do not have active suicidal intent indicating significant clinical risk (which would suggest that a treatment specifically targeting this intent was indicated); (12) do not have a major medical condition likely to significantly impact cognitive functioning such as stroke, multiple sclerosis, Parkinson's, brain tumor, or congestive heart failure; (13) are not currently participating in any type of brain stimulation treatment; and (14) are between the ages of 18 to 75 years old. To maximize the generalizability of the study and ensure that we are testing CCT with a typical PTSD Veteran population, exclusion criteria are minimized (e.g., there are no medication exclusion criteria, and Veterans with comorbid depression or anxiety disorders will be included). Current cognitive functioning deficits are also required for participation, and chart review and NSI screening will be implemented for this study.

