health clinics. With approval of the clinical providers, additional eligibility screening will take place for up to 120 Veterans; the Veterans who meet eligibility criteria will be contacted until the desired sample size of 36-48 participants are enrolled in the study. There is currently a waiver of informed consent to be able to review Veterans' medical records to ensure medical inclusion and exclusion criteria are met prior to contacting potentially eligible Veterans. This may reduce time and travel burden for Veterans who do not meet these minimum study criteria. [name] or another study member will let VA mental health clinicians know about the study and inclusion/exclusion criteria and request their assistance in recruiting eligible Veterans. This information will be provided to clinicians in the form of an email, in person conversation, team meeting presentation, or phone call using the attached email letter/script. Veterans meeting these study criteria will be informed of the study by their clinician from the mental health clinic in which they receive mental health treatment. If they are willing to participate, the clinician will notify [name] through CPRS, encrypted email, or in person meeting, or phone call that the Veteran agreed to be contacted about the study. Veterans who express interest in participating will be called to schedule a meeting to discuss and obtain informed consent and to conduct the 90-minute baseline assessment and be randomized to CCT or TAU group if they consent to study participation. During the initial scheduling call, Veterans will be given the option to conduct the baseline visit (i.e., discuss and obtain informed consent and conduct the 90-minute baseline assessment) in person, via VVC, or via telephone; staff will follow current VA guidance about inperson visits and will allow for participant preference when permitted by the VA (e.g., if the Portland VA does not recommend in-person for non-essential visits, then this option will not be offered, and only VVC or telephone appointments will be offered).

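### Whole groups of six are randomised, but no planned analysis names the group, and the stated TAU groups do not add up to the upper sample size

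*Combined protocol and SAP*

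**What the plan says.** **Unit of randomisation.** Randomization and Blinding puts new participants into a waiting group and then states: "Once group membership reaches 6 participants, the group will be randomized by the statistician". The same section opens with "All eligible participants will be randomized to either the CCT or TAU group". Informed Consent & HIPAA Authorization describes a meeting at which Veterans consent, complete the baseline assessment and "be randomized to CCT or TAU group if they consent to study participation". The last two read as allocation one person at a time.

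**Numbers.** The section on study setting and sample size gives a total of 36 to 48. Inclusion/Exclusion Criteria gives about 4 to 5 CCT groups of six and "12-18 TAU participants, grouped for randomization piloting purposes into 6-Veteran participants in each of 2 groups".

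**Delivery.** CCT is run as a weekly group over 10 weeks (Intervention; Enrollment and Assessment Procedures). For the control arm, "TAU will consist of routine, weekly mental health psychotherapy".

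**Analysis.** Clinical and Functional Outcome Analyses states: "Primary outcome analyses will be multilevel models to compare the change over time in cognitive, mental health, functioning, and QOL outcomes for Veterans". The levels of these models are not given. If the sample is too small, "we will run alternative methods such ANOVAs which are more feasible with smaller samples". The same section says that the significance of between-group differences will be examined, that the effect sizes will be used for the power and sample size of the full trial, and that suitable assumptions will be made in doing so. No ICC, design effect or group-level degrees of freedom appears anywhere.

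**The concern.** The unit that is randomised sets the error term for comparing arms. Here it is a group of six, and in the CCT arm the same six people are also treated together. Members of a group may therefore resemble each other more than members of different groups. An analysis that treats 36 to 48 Veterans as independent ignores this.

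Aim 2's product is an effect size for planning the full trial. Ignoring the group hardly moves that estimate, but it overstates its precision and inflates the between-arm tests. The full trial would be too small only if it is also group-randomised or group-delivered, the ICC is above zero, and no design effect is applied. The feasibility conclusions are not affected.

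The mixed wording on the unit of randomisation adds to the problem, because the statistician cannot tell from the text which analysis matches the design.

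**Working it through.** **1. Counts.**
- Lower end: 4 × 6 + 2 × 6 = 24 + 12 = 36, which agrees with the plan.
- Upper end with the stated 2 TAU groups: 5 × 6 + 2 × 6 = 30 + 12 = 42, not 48, and TAU is 12, not 18.
- Reaching 48 with 5 CCT groups needs 48 − 30 = 18 TAU Veterans, which is 3 groups.
- Randomised units: 36/6 = 6 to 48/6 = 8.

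**2. Inputs for clustering.** Group size is 6. The layouts are 4 v 2, 5 v 2 and 5 v 3 groups (CCT v TAU). The ICC is an assumption, 0.01 to 0.20, because the documents give none. Total SD is set to 1. TAU is routine care without shared delivery, so clustering in CCT only is the milder case.

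**3. Standard error and degrees of freedom.** The design effect is 1 + (6 − 1) × ICC, which gives 1.05, 1.25, 1.50 and 2.00 at ICC 0.01, 0.05, 0.10 and 0.20.
- Both arms clustered: the true standard error exceeds the individual-level one by the square root of the design effect, a factor of 1.02, 1.12, 1.22 and 1.41.
- CCT only, 24 v 12, ICC 0.10: √[(1.5/24 + 1/12) / (1/24 + 1/12)] = √(0.1458/0.1250) = 1.08.
- Degrees of freedom: 36 − 2 = 34 by individual against 6 − 2 = 4 by group (critical t 2.032 against 2.776). With 48 Veterans they are 46 against 6 (2.013 against 2.447).

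**4. True type I error of a nominal 5% individual-level t-test.** Simulation, 60,000 trials per cell, no true effect; ranges run over the three layouts.

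| ICC | CCT only | Both arms |
|---|---|---|
| 0.01 | 5.1–5.2% | 5.5–5.8% |
| 0.05 | 6.0–6.2% | 8.0–8.2% |
| 0.10 | 6.8–7.4% | 11% |
| 0.20 | 8.7–9.7% | 17–18% |

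A true standardised difference of 0.50 is estimated on average as 0.51 to 0.53, so bias is small.

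**5. Mean width of the 95% interval at ICC 0.10, in SD.**

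| Layout | Clustering | Individual level | Group means |
|---|---|---|---|
| 4 v 2 | CCT only | 1.41 | 2.15 |
| 4 v 2 | Both arms | 1.41 | 2.26 |
| 5 v 3 | CCT only | 1.19 | 1.61 |
| 5 v 3 | Both arms | 1.18 | 1.72 |

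**6. Behaviour of the remedies.**
- A t-test on group means rejects 4.8–5.2% of the time if both arms cluster, and 3.0–4.5% at ICC 0.05–0.20 if only CCT does.
- A random-intercept model with df = groups − 2 and its group variance cut off at zero rejects only 0.6–4.0%.
- At a true ICC of 0.05, the pilot's own ICC estimate is zero or negative in 39–47% of trials.

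**7. Consequence for a full trial (illustration).** Assume d = 0.5, 80% power, 1:1 allocation and groups of six. Without clustering, N = 2 × 63.8, or 128. At ICC 0.01, 0.05, 0.10 and 0.20:
- both arms grouped, × (1 + 5 × ICC): 134, 160, 192, 256;
- CCT only grouped, × (2 + 5 × ICC)/2: 131, 144, 160, 192.

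**The case against.** The strongest reply is that this is a deliberately underpowered pilot. It promises effect sizes, not confidence intervals, and the effect size is nearly unbiased. The plan says pilot estimates should not be the sole basis for planning and compares them with the earlier mild TBI trial. The multilevel models might include the group, and an ANOVA might be nested; the plan is silent rather than wrong. These points limit the consequence. They do not remove it, because between-arm significance is to be examined, and silence leaves the individual-level analysis as the natural reading.

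Clustering may also be slight. TAU groups exist only for allocation, and CCT may be taken by video or telephone. The calculations use a single-time-point t-test, whereas the plan analyses change, whose ICC may differ. All of this bears on which ICC is realistic. None of it alters the unit that is randomised.

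Finally, group means are wasteful if only CCT clusters. A partially nested comparison (CCT group means against individual TAU Veterans, Satterthwaite df) then rejects 4.7–5.0% of the time, and at ICC 0.10 its interval is 1.68 SD (4 v 2) or 1.39 SD (5 v 3), against 2.15 and 1.61 by group means. That is a real gain, so the individual-against-group-means gap overstates the unavoidable loss in that case. But the method rejects about 6–11% at ICC 0.05–0.20 if TAU groups cluster too, and 2 or 3 TAU groups are too few to settle whether they do. Matching the analysis to the randomised unit is safer.

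**Conclusion.** The concern holds. The group rule makes the trial one of 6 to 8 units, and the analysis text does not provide for them. The size depends on an ICC that the documents do not give. At ICC 0.01 the effect is negligible. At 0.10 a nominal 5% test runs at about 7% (CCT only) or 11% (both arms), and the individual-level interval is well short of one based on groups. The ICC meant is that of the outcome as analysed, including change scores. That the ANOVA is individual-level is inferred from the absence of any group term.

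The TAU count fails at its upper end whatever the ICC. The point should be fixed, but it concerns how results are carried forward to the full trial, not whether the pilot can meet its feasibility aim.

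**What to change.** 1. **Clinical and Functional Outcome Analyses, models.** Add the randomised group as a random effect in every between-arm model, with df = number of groups − 2 (4 to 6), and allow the group variance to be estimated below zero. Replace the ANOVA fallback with a comparison of group means.
2. **Same section, effect sizes and planning.** Report effect sizes with group-adjusted intervals. If the full trial will be grouped, show its sample size over a range of ICCs, applying the design effect only to the arm or arms that cluster. Do not rely on the pilot's own ICC estimate.
3. **Inclusion/Exclusion Criteria.** Restate TAU as 2 to 3 groups of six.
4. **Randomization and Blinding; Informed Consent & HIPAA Authorization.** Reconcile the participant-level wording with group allocation.

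The cost is rewording and a little more analysis; allocation and sample size do not change. Intervals become wider. If the true ICC is 0, the group-mean interval averages 1.85 SD against 1.43 SD with 4 v 2 groups (about 29% wider than needed) and 1.40 against 1.19 SD with 5 v 3 (about 17%, from unrounded widths).

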Study setting, sample size, and recruitment feasibility: The proposed study is conducted at a single site. We propose to enroll at least 36, and up to 48, total Veterans in this pilot RCT. Because our primary purposes are to examine feasibility of this clinic-based research and acceptability to Veterans with PTSD and estimate effect sizes for a future fully powered RCT. achieving adequate statistical power is not a primary concern of this pilot clinical trial. Results from this pilot RCT with a sample size of 36 to 48, combined with comparisons to similar studies of CCT with other Veteran groups (e.g., those with mild TBI history), will provide adequate information on expected effect size to allow for estimations of statistical power for a future RR&D Merit proposal of a fully powered RCT. VHAPORHCS Mental Health and PTSD clinics will serve as primary sites for study recruitment, assessment, and intervention activities. We will work with the Public Affairs Office to post IRB approved study flyers in VHAPORHCS Mental Health and PTSD clinics and nearby elevators as well as the main hospital. The flyers provide information about the study and will help notify Veterans of the opportunity to participate in this study. Eligibility and recruitment procedures used to identify Veterans who report residual cognitive functioning deficits following recent (past year) treatment for PTSD at the Portland VA will be used to recruit Veterans for this pilot trial. Veterans who have participated in PTSD treatment and report cognitive functioning deficits on the Neurobehavioral Symptom Inventory (NSI; moderate cognitive symptoms or greater on any cognitive functioning item), will be recruited from the clinics.

CDW: If needed to achieve recruitment goals, we will also access the VA's Corporate Data Warehouse (CDW) and use ICD-10 codes to identify Veterans with recent (past year) Portland VA mental health or PTSD clinic treatment for PTSD. NSI data is also available for some Veterans in CPRS and Veterans with elevated NSI scores or neuropsychological evaluations

9

will be prioritized for recruitment. The CDW will be used to identify potentially eligible Veterans. The Veterans' clinicians will be contacted to ask them if they would like to refer these identified Veterans to the study. If the clinician wants to refer a Veteran to the study, this will be documented and the IRB approved recruitment procedures for a referred Veteran will then be followed.

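### The recruitment-feasibility rule uses two percentages and is not tied to the plan's own minimum of 36 enrolled, so it can be met when that minimum is missed

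*Combined protocol and SAP*

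**What the plan says.** The rule is in Study Feasibility Analyses: "Recruitment will be deemed feasible if we successfully screen for eligibility 50% of Veterans referred to the study and enroll 75% of screened Veterans". The sentence then restricts the 75% to screened Veterans who satisfy all inclusion criteria. The two conditions are therefore screened/referred (50%) and enrolled/eligible (75%).

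The enrolment target appears in other sections. Study setting, sample size, and recruitment feasibility says: "We propose to enroll at least 36, and up to 48, total Veterans in this pilot RCT". Inclusion/Exclusion Criteria repeats it: "Participants will be at least 36 (and up to 48) Veterans weighted with more CCT participants", made up of "approximately 4-5 CCT groups with 6 Veterans each) than controls (12-18 TAU participants". Informed Consent & HIPAA Authorization says that eligible Veterans "will be contacted until the desired sample size of 36-48 participants are enrolled in the study", and the CDW paragraph adds a data-warehouse route in case recruitment falls behind.

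Feasibility and Acceptability commits to recording the numbers referred, screened, enrolled and completing, with reasons for ineligibility and for eligible Veterans not enrolling. It attaches no threshold to these counts.

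On retention, Study Feasibility Analyses says: "Retention will be deemed successful if we achieve 80% completion for post-treatment assessments". Feasibility and Acceptability measures retention by assessments completed no more than two weeks from the target date.

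**The concern.** Recruitment feasibility is part of Aim 1, and feasibility is the first hypothesis. A rule fixed in advance should be able to fail when recruitment falls short of what the plan set out to achieve. This one cannot fail on numbers alone, because a percentage of a small pool can be as high as a percentage of a large one. The minimum of 36 is stated as a target but is not an input to the verdict.

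At stake is a pre-stated conclusion that recruitment was feasible, standing beside counts that show the target was missed. A team planning the larger trial should not have to choose between the two.

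**Working it through.** **Inputs.** Thresholds of 50% and 75% (Study Feasibility Analyses); enrolment of 36 to 48 (Study setting, sample size, and recruitment feasibility; Inclusion/Exclusion Criteria); CCT in 4 to 5 groups of 6, and 12 to 18 TAU participants (Inclusion/Exclusion Criteria); retention threshold of 80% (Study Feasibility Analyses). The numbers referred, screened and eligible used below are assumed for illustration.

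**1. The plan's own total.** Minimum: 4 × 6 + 12 = 36. Maximum: 5 × 6 + 18 = 48. Both reproduce.

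**2. Smallest enrolment that passes.** If E Veterans are eligible, the second condition needs at least 0.75 × E enrolled. Setting 0.75 × E = 36 gives E = 36/0.75 = 48.
- With 48 or more eligible, passing the 75% condition guarantees at least 36 enrolled.
- With 36 to 47 eligible, the rule can pass with fewer than 36.
- With fewer than 36 eligible, the minimum cannot be reached even at full uptake, yet the rule can still pass.

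**3. A passing case at half the minimum.** 72 referred, 36 screened, 24 eligible, 18 enrolled.
- Screened/referred = 36/72 = 50%: met.
- Enrolled/eligible = 18/24 = 75%: met.
- Enrolled/minimum = 18/36 = 50%.

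**4. The same at larger screening volumes (eligible shares assumed).**
- 120 screened, 30% eligible: 36 eligible, 27 enrolled, 27/36 = 75%. Passes with 27.
- 500 screened, 8% eligible: 40 eligible, 30 enrolled, 30/40 = 75%. Passes with 30.

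**5. Enrolled and randomised can differ.** Under Randomization and Blinding, "Once group membership reaches 6 participants, the group will be randomized by the statistician". Veterans waiting in an incomplete group are enrolled but not yet randomised, so both counts should be reported.

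**6. Retention (secondary).** At N = 36, 0.80 × 36 = 28.8, so 29 completers are needed: 29/36 = 80.6% passes and 28/36 = 77.8% fails. One completer outside the two-week window can therefore decide the verdict, which is why the protocol should say whether the window applies.

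**The case against.** The strongest reply is that the passing cases are constructed. The plan has no provision for stopping at 18. It means to go on contacting eligible Veterans until 36 to 48 are enrolled and holds a data-warehouse search in reserve. The percentages are process rates that carry over to a larger trial, and a shortfall would be plain in the counts the plan already collects. Most of this stands. The rates are legitimate and the 75% criterion should stay. But continuing to recruit is an intention; whether it succeeds is what a feasibility criterion tests, and this rule would not register failure.

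The reply also notes, rightly, that a floor of 36 without a time limit has little force when recruitment simply continues until 36 is reached. The fix therefore includes a recruitment period.

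A reader might draw four stronger conclusions that the documents do not support.

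- **That Aim 2 loses its basis below 36.** The sentence that begins "Results from this pilot RCT with a sample size of 36 to 48" goes on to combine the pilot with comparisons to similar CCT studies, and Clinical and Functional Outcome Analyses warns against relying on small-pilot effect sizes alone. Nor is 36 a point at which precision becomes adequate. Ignoring clustering and assuming a 2:1 split, the approximate 95% half-width for a standardised difference is 1.96 × √(1/24 + 1/12) = 0.69 at 36, against 1.96 × √(1/12 + 1/6) = 0.98 at 18.
- **That the eligible share is lost.** It can be derived from the records listed in Feasibility and Acceptability. It is only absent from the rule, and descriptive reporting is enough.
- **That the two screening figures conflict.** Enrollment and Assessment Procedures anticipates up to 500 screened; Informed Consent & HIPAA Authorization gives up to 120 for additional eligibility screening. These may be different stages, so they need labels.
- **That the retention threshold contradicts the two-week measure, or hides a failing arm.** The window can reasonably be read into the threshold. A split such as 24/24 CCT with 5/12 TAU (together 29/36) is a worst case, by-arm display is not ruled out, and Participant retention/ Dropout Minimization reports retention above 90% in recent CCT trials.

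**Conclusion.** The point holds in a limited form. As written, recruitment can be declared feasible with fewer than 36 enrolled whenever fewer than 48 Veterans are found eligible; the worked case passes at 18, half the minimum. This follows from the wording and arithmetic alone. That it would happen in this trial is not shown: it needs referrals or time to run out first, and the documents do not say how likely that is.

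The consequence is an Aim 1 verdict at odds with the plan's own target. No section makes the follow-on proposal depend on that verdict, and no argument about power is involved. The change is still worth making because it costs almost nothing and alters a conclusion fixed in advance. The retention and screening items are clarifications.

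**What to change.** In Study Feasibility Analyses, keep both percentages and add the minimum and a time limit, for example: *recruitment is judged feasible when both percentages are reached and no fewer than 36 Veterans have enrolled by the end of the planned recruitment period.* The sponsor should state that period. Beside the verdict, report the number randomised and the eligible share of those screened, both descriptively and without a threshold.

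Clarifications:
- State that the 80% post-treatment retention threshold uses the two-week window in Feasibility and Acceptability, and show completion by arm descriptively.
- Define the stage that screening refers to in the recruitment rule, and the stages to which the figures of up to 500 and up to 120 belong.

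Cost: a few sentences and some extra tabulation from records already planned, with no new visits or measures. The downside is that the recruitment criterion becomes somewhat harder to meet. An assessment completed outside the window would no longer count towards the 80%, although its data could still be analysed.
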